### 7.6.1 Non- Hematologic Toxicity

Non- Hematological dose limiting toxicity is defined as any Grade 3 or greater non-hematological toxicity attributable to the investigational drug with the specific exclusion of:

- Grade 3 nausea and vomiting of less < 3 days duration.
- Grade 3 liver enzyme elevation, including ALT/AST/GGT that returns to levels that meet initial eligibility criteria or baseline within 7 days.
- Grade 3 or 4 fever < 5 days duration.
- Grade 3 infection < 5 days duration.
- Grade 3 hypophosphatemia, hypokalemia, hypocalcemia or hypomagnesemia responsive to supplementation.
- Any Grade 2 non-hematological toxicity that persists for  $\geq 7$  days and is considered sufficiently medically significant or sufficiently intolerable by patients that it requires treatment interruption.
- **Note:** Allergic reactions that necessitate discontinuation of study drug will not be considered a dose-limiting toxicity.

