#### **11.2 Period of Observation**

Following the subject’s written consent to participate in the study, all SAEs must be collected, including those thought to be associated with protocol-specified procedures. Collection of all SAEs must continue for **30 days** after the last administration of the investigational product. If applicable, SAEs must be collected that relate to any later protocol-specified procedure (e.g., a follow-up skin biopsy). The investigator should notify the DISC of any SAE occurring after this time period that is believed to be related to the investigational product or protocol-specified procedure.

The investigator will begin collecting non-serious adverse event (NSAE) information once administration of the investigational product is initiated. This NSAE information should also be collected from the start of a placebo lead-in period or other observational period intended to establish a baseline status for the subjects. Treated subjects, including those who were prematurely discontinued from the study, will be followed for any adverse events that occur during the study until 30 days following the last dose of study treatment (i.e., the Follow-up Visit). However, if another course of anti-cancer therapy is initiated prior to the 30-day follow-up

period visit, collection of adverse events will no longer be performed, with the exception of events that may be possibly, probably, or definitely related to the investigational agent or are clinically significant.

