#### **11.3.1 Assessment of Causal Relationship of Study Drug**

The Investigator will provide an assessment of the potential causal relationship between adverse events and study medication by determining whether or not there is a reasonable possibility that the event was caused by the study medication. The relationship or association of the adverse event to the study medication will be characterized as not related, unlikely related, possibly related, probably related, or related:

**Not Related:** There is not a temporal relationship to the study drug administration or the adverse event is clearly due only to the progression of the underlying disease state, intercurrent illness, concomitant medication, concurrent therapy or other known cause.

**Unlikely Related:** There is little or no chance that the study drug

administration caused the adverse event; the event is most likely due to another competing cause, including intercurrent illness, progression or expression of the disease state, or a reaction to a concomitant medication or concurrent therapy appearing to explain the reported adverse event.

**Possibly Related:** The association of the adverse event with the study drug administration is unknown; however, the adverse event is not reasonably attributed to any other condition.

**Probably Related:** When a reasonable temporal relationship exists between the adverse event and the study drug administration; significant symptoms abate upon discontinuation of the study drug and there is a reasonable explanation based on known characteristics of the study drug and there is no clear association with preexisting disease or therapy, intercurrent illness, concurrent therapy or other factor(s).

**Related:** When the adverse event is a known side effect of the study drug or there is a temporal relationship to the administration of the study drug; or the adverse event reappears upon re-administration of the study drug (rechallenge); or the significant symptoms of the adverse event abate upon discontinuation of the study drug (dechallenge).

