#### **12.6 Analysis of Safety Data**

The incidence, severity and reversibility of toxicities will be performed on all subjects who receive any dose of study medication. Non-serious adverse events that occur more than 30 days after the administration of the last dose of treatment will not be included. The safety and tolerability of treatment is determined by reported AEs, physical examinations, and laboratory tests.. AEs will be summarized with the incidence and percentage of subjects with at least one occurrence of a preferred term (NCI - CTCAE Version 5 grade) will be included. The number of AEs reported will also be summarized. Causality (relationship to study drug) will be summarized separately. Duration of AE will be determined and included in listings along with action taken and outcome.

Laboratory results will be classified according to NCI-CTCAE, Version 5.0. Incidence of laboratory abnormalities will be summarized; laboratory results not corresponding to an NCI- CTCAE Version 5.0 term will not be graded. Laboratory toxicity shifts from baseline to worst grade will also be provided. The results from physical examination and vital sign measurement will be tabulated.

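### In Section 11.3.1 the top causality category, Related, is looser than Probably Related and overlaps with Not Related, with no precedence rule, so the causality summary can over-attribute events to the drug

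*Combined protocol and SAP*

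**What the plan says.** Section 11.3.1 asks the investigator whether there is a reasonable possibility that the drug caused the event, and then offers five labels.

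- *Related*: the event is a known side effect, "or there is a temporal relationship to the administration of the study drug", or it returns on rechallenge, or its main symptoms abate on dechallenge.
- *Probably Related*: a reasonable temporal relationship, abatement on stopping, an explanation from the drug's known characteristics, and no clear link to another factor, all together.
- *Possibly Related*: the association is unknown, but "the adverse event is not reasonably attributed to any other condition".
- *Unlikely Related*: little or no chance that the drug was the cause; a competing cause is most likely.
- *Not Related*: no temporal relationship, or wholly caused by something else.

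Temporal relationship is not defined, and nothing says which label applies when two fit. By contrast, Section 11.3.3 does give a worst-case hierarchy for action taken with study drug.

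Section 12.6 uses the result: "Causality (relationship to study drug) will be summarized separately". It does not say which categories would be pooled as treatment-related. Section 11.2 continues collection after new anti-cancer therapy for events that may be "possibly, probably, or definitely related to the investigational agent". The last of those labels is not among the five.

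**The concern.** A causality scale should become harder to satisfy as it rises. Here the top step is easier than the two below it: *Possibly Related* and *Probably Related* both test for another cause, and *Related* does not.

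The design makes this matter. Dosing is twice daily in continuous 28-day cycles for up to 26 cycles (Sections 3.1 and 7.2). Non-serious events are collected only from first dose to 30 days after last dose (Section 11.2). The known-side-effect condition adds to the problem. Section 10.1.7 lists pain, fatigue, nausea, decreased appetite, vomiting and constipation as the most common reactions, and advanced sarcoma can produce several of these itself. With a single arm there is no concurrent control rate against which over-attribution would show.

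At stake is whether the by-causality summary can be interpreted, and whether two investigators following the same text would code the same event alike.

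**Working it through.** The plan gives no figure to reproduce; the check is of the logic of the definitions.

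**Inputs (Section 11.3.1).** Seven yes/no features: K known side effect, T temporal relationship, R positive rechallenge, D positive dechallenge, E pharmacological explanation, A clear association with another factor, O due only to another cause. O implies A, so the pair (A, O) has 3 admissible values. Admissible patterns: 2^5 × 3 = 96.

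**Rules as written.**
- *Related* = K or T or R or D
- *Probably Related* = T and D and E and not A
- *Not Related* = (not T) or O

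*Possibly Related* and *Unlikely Related* rest on judgement and are not coded.

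**Results.**

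| Patterns | Number | Also *Related* |
|---|---|---|
| T present | 2^4 × 3 = 48 | 48 |
| T present; K, R and D absent | 2 × 3 = 6 | 6 |
| *Probably Related* (K and R free) | 2^2 = 4 | 4 |
| T present and O present (*Not Related*) | 2^4 = 16 | 16 |
| All *Not Related* | 48 + 16 = 64 | 64 − 6 = 58 |

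The 6 subtracted in the last row are the patterns with none of K, T, R and D. *Probably Related* therefore sits wholly inside the category above it, and *Not Related* overlaps with *Related*. These are counts of logical patterns, not of patients or events. They show how the rules relate and say nothing about how often events would be miscoded.

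**Candidate repairs.**

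1. Join K and T by *and*: *Related* = (K and T) or R or D. The 6 timing-only patterns drop out, so 48 − 6 = 42 temporal patterns still qualify. All 4 *Probably Related* patterns remain *Related*, through D.
2. T and (K or D or R) and no likelier cause. Timing alone no longer suffices. But each of the 4 *Probably Related* patterns has T and D and no clear other association, so all 4 still qualify and the inversion remains.
3. *Related* = *Probably Related* and (K or R). Of the 4 patterns, 3 have K or R and become *Related*; 1 stays *Probably Related*. *Related* is now the narrower category. Overlap with *Not Related* is 0, because *Probably Related* needs T and not A, whereas *Not Related* needs not T, or O, which implies A.

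Only the third restores the order.

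**The case against.** The strongest defence is that the labels only record the judgement requested in the opening sentence of Section 11.3.1. An investigator who sees no reasonable possibility of drug causation has *Not Related* and *Unlikely Related* available, and both name disease progression. Disease-caused pain or fatigue already has a place, and experienced investigators may well code sensibly. This stands as a limit on how much harm to expect. It does not repair the text: the opening question has a yes-or-no answer and does not choose among overlapping labels.

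A reader might infer that essentially every on-treatment event would be coded *Related*. The documents do not support that as a forecast. It equates being on drug with an undefined temporal relationship. If that were the meaning, the no-temporal-relationship part of *Not Related* would be nearly empty for non-serious events, so a narrower meaning is plausible. A narrower meaning does not remove the defect, however. The nesting and overlap hold for any event that does have a temporal relationship, and the known-side-effect condition needs no timing at all.

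A reader might also infer that these categories decide what counts as a dose-limiting toxicity. Section 7.6.1 speaks of "any Grade 3 or greater non-hematological toxicity attributable to the investigational drug" but cites neither Section 11.3.1 nor any of the five labels. The hematological definition in Section 7.6.3 has no drug-attribution condition; its Grade 4 item excludes only malignant infiltration. Section 12 contains no analysis or stopping rule based on a dose-limiting toxicity rate.

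**Conclusion.** The point holds as a defect of definition. As written, the causality scale is out of order and its categories are not mutually exclusive. Literal use would push the Section 12.6 causality summary towards over-attribution. This rests on the plain reading of *or* in the *Related* definition and on the absence of a precedence rule.

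The direction is clear for literal application, but the size cannot be computed from the documents, because it depends on how investigators read temporal relationship and how far they rely on the opening sentence. It would go too far to say that the treatment-related results will be wrong, that nearly all events will be coded *Related*, or that dose-limiting toxicity is determined by this scale. Overall adverse event incidence, ORR, PFS, TTP, CBR and the pain score do not use the causality label and are unaffected.

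**What to change.** In Section 11.3.1:

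- Redefine *Related* as meeting every condition of *Probably Related* plus at least one more: known side effect of the drug, or positive rechallenge.
- State that an event explained by another cause under *Not Related* or *Unlikely Related* cannot be coded *Related*.
- State that otherwise the highest category whose conditions are all met is assigned.

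In Section 11.2, replace the label definitely related with related, so that the terms match the five categories.

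The cost is a short amendment, CRF completion guidance and a re-check of events already coded, in at most 50 enrolled subjects (Section 4.1). One consequence should be accepted knowingly. *Probably Related* requires improvement after stopping the drug, so an event without dechallenge information can reach neither of the top two categories. If no other condition reasonably explains it, it would be coded *Possibly Related*.

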#### 11.3.2 Intensity of Adverse Events

The intensity of adverse changes in physical signs or symptoms will be graded according to the most up-to-date CTCAE version. For all other adverse events not described in the CTCAE, the intensity will be assessed by the Investigator using the following categories:

**Mild** (Grade 1) – transient or mild discomfort; no limitation in activity; no medical intervention/therapy required.

**Moderate** (Grade 2) – mild to moderate limitation in activity, some assistance may be needed; no or minimal medical intervention/therapy required.

**Severe** (Grade 3) – marked limitation in activity, some assistance usually required; medical intervention/therapy required, hospitalization is possible.

**Life-threatening** (Grade 4) – extreme limitation in activity, significant assistance required; significant medical intervention/therapy required, hospitalization or hospice care probable.

**Death** (Grade 5) – the event resulted in death.

#### **11.3.3 Action Taken with Study Drug**

The action the Investigator took with study drug as a result of the event should be recorded as one of the following:

**None** – No action was taken with regard to the study drug as a result of the adverse event.

**Interrupted** – Study drug was stopped due to the adverse event, but was later resumed at the same dose.

**Dose decreased** – The dose of study drug was decreased as a result of the adverse event.

**Permanently discontinued** – The subject was withdrawn from the study due to the adverse event.

Only one item should be chosen. If multiple actions apply, the following “worst case” scenario hierarchy should be used to determine the preferred entry: permanently discontinued > dose decreased > interrupted.

#### **11.3.4 Definition of Outcome**

The outcome of the AE should be recorded as one of the following:

**Resolved without sequelae** – The subject fully recovered from the adverse event with no observable residual effects.

**Resolved with sequelae** – The subject recovered from the adverse event with observable residual effects.

**Not resolved** – The adverse event was present at the time of last observation.

**Death** – The subject died as a result of the adverse event.

### **11.4 Immediately Reportable Events**

#### **11.4.1 Serious Adverse Events**

Serious adverse events (SAE's) must be reported to the UFHCC CRO Project

Management Office (PMO; [[contact]](mailto:[contact])), and entered into OnCore, within **24 hours** of discovery of the event. The FDA MEDWATCH 3500 form must be completed and sent to Epizyme within **7 business days**. If only limited details are known, these should be reported within that time frame and follow up reports can be submitted for elaboration, clarifications, or corrections. Any email correspondence must be kept in the trial file at the study site. The site investigator is responsible for informing the IRB and/or the Regulatory Authority of the SAE as per local requirements.

Follow-up information will be submitted to the UFHCC CRO PMO ([[contact]](mailto:[contact])), stating that this is a follow-up to a previously reported SAE and giving the date of the original report. Each re-occurrence, complication, or progression of the original event should be reported as a follow-up to that event regardless of when it occurs. The follow-up information should describe whether the event has resolved or continues, if and how it was treated, and whether the participant continued or withdrew from study participation. PMO will confirm that the event and any necessary follow-ups are reported to the UFHCC Data and Safety Integrity Committee (DISC), the sponsor, and any other regulatory authorities as required (FDA, etc.)

#### 11.4.2 Other Events Requiring Immediate Reporting

All pregnancies, regardless of outcome, must be reported to the UFHCC CRO Project Management Office (PMO; [[contact]](mailto:[contact])), including pregnancies that occur in the female partner of a male study subject. All pregnancies must be followed to outcome. Pregnancies and follow-ups will be submitted by PMO to DISC, the sponsor if required, and any other regulatory authorities required.

Although overdose and cancer are not always serious by regulatory definition, these events should also be reported to the UFHCC CRO Project Management Office (PMO; [[contact]](mailto:[contact])) in an expedited manner. In case the overdose did not result in any adverse event, the Investigator should report this as "overdose, no adverse event" and provide the intended amount, as well as the actual amount, of drug administered. In the event of overdose or exaggerated response, appropriate supportive measures should be employed. Actual treatment should depend on the severity of the clinical situation and the judgment and experience of the treating physician. Overdose events and follow-ups will be submitted by PMO to DISC, the study sponsor if required, and any other regulatory

authorities required.

Pregnancies and overdoses should be documented and reported per the reporting guidelines below.

Institution Immediate Reporting Information
SAEs and pregnancies must be reported to the UFHCC CRO Project Management Office (PMO), or assigned designee at:  Email: [contact] As well as entered in OnCore, the study CTMS.

#### 11.4.3 Reporting to Epizyme

The UFHCC CRO Project Management Office (PMO) will forward any SAE, AESI, or pregnancy to Epizyme as agreed upon in the contract. PMO will forward both initial and follow-up versions of each report.

Epizyme AE and Pregnancy Reporting Information
Email: [contact] AND [contact]

## 12. STATISTICAL METHODS

The sections below provide an overview of the statistical considerations and analyses.

### 12.1 Data collection and management plan

Data will be collected via paper source documents and the medical record, and will subsequently be entered into a validated Electronic Data Capture (EDC), REDCap, which will be monitored and audited on a regular basis to ensure accuracy. Data will be accessible only to certified members of the research team, under the supervision of the PI, and will be fully de-identified prior to analysis. All paper records will be archived for a pre-specified length of time as per applicable regulations and federal laws.

### 12.2 Sample Size Justification

Simon's two-stage Optimum design will be used for the study to evaluate the primary endpoint of objective response rate (ORR, defined as CR+PR) of Tazemetostat. Assuming that with current treatment (traditional chemotherapy with doxorubicin and ifosfamide), ORR is 21% for the target study subjects (*Kroep*

*JR et al Annals Oncol 22:207-214, 2011*), the null hypothesis that the true ORR is 21% and this will be tested against a one-sided alternative. In the first stage, 9 patients will be accrued. If there are 2 or fewer responses in these 9 patients, the study will be stopped. Otherwise, 20 additional patients will be accrued for a total of 29. The null hypothesis will be rejected if 10 or more responses are observed in 29 subjects. This design yields a type I error rate of 5% and power of 80% when the true ORR is 45%.

Assuming an enrollment rate of 6-12 subjects per year per institutional experience, this protocol is expected to accrue within 2-4 years.

#### 12.3 Analysis of Primary Endpoint

The analysis for the primary endpoint, ORR, is based on the intent-to-treat approach. ORR will be calculated as the proportion of the patients with objective response divided by the total number of the study patients. The 95% confidence interval for ORR will be calculated based on the exact binomial distribution.

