**STUDY SCHEMA – SINGLE ARM**

Cycle = 28 days

Accrual Goal: 29 evaluable subjects (Up to 50 total accrued)

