## PROTOCOL SYNOPSIS

Title:	Phase 2 study using Tazemetostat in patients with recurrent/refractory and/or metastatic malignant peripheral nerve sheath tumors (MPNST)
Funding Source(s):	Epizyme, University of Florida
Investigational Agent Source:	Epizyme
Rationale:	
Enhancer of zeste homolog 2 (EZH2) is a critical component of polycomb repressive complex 2 (PRC2), a multimeric protein complex which plays an essential role in the epigenetic maintenance. EZH2 has been shown to be a critical regulator of epithelial-mesenchymal transition, which is a critical step for initiation of cancer invasion and metastasis.
 
Recent research showed that EZH2 expression is significantly higher in MPNST than in neurofibromas and normal nerve tissues. EZH2 knockdown by RNA interference in MPNST cell lines induces MPNST cell apoptosis in vitro and inhibits MPNST tumor growth in vivo. Pharmacological inhibition of EZH2 has been shown to inhibit MPNST cell growth and induce apoptosis in vivo, in vitro and in mouse xenograft models. In addition, inhibition of EZH2 has been shown to ameliorate MPNST invasion and metastasis. These preclinical data suggest that EZH2 is a potential therapeutic target in MPNST.

Objectives:	
Primary:
 
To assess the objective response rate of Tazemetostat in subjects with recurrent/refractory and/or metastatic MPNST.
 
Secondary:
 
 
• To determine the progression free survival (PFS) in subjects with recurrent/refractory and/or metastatic MPNST.
 
• To determine the time to progression (TTP) in subjects with recurrent/refractory and/or metastatic MPNST.
 
• To determine the clinical benefit using subject reported outcome (PRO)
 
• To assess the clinical benefit rate (CBR).
 

	
Exploratory aims:
 
 
• Assess circulating tumor DNA (ctDNA) as a potential treatment response tool
 
• Correlate clinical data, outcomes and toxicity with biomarkers of EZH2 inhibition and resistance, potentially including but not limited to circulating or tumor molecular profiling, epigenetics, and immune system activity.
 

Study Design:	This is a single institution, single-arm, open label phase 2 study.
Accrual Goal:	Up to 50 people will be enrolled in this study to achieve 29 evaluable subjects.

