### 3. STUDY DESIGN

#### 3.1 Study Overview

This is a single institution, open label, single-arm phase 2 trial. We plan to accrue up to 50 subjects in order to meet our goal of 29 evaluable subjects. Each subject will be administered Tazemetostat orally twice daily for subjects with recurrent and/or metastatic MPNST. Subjects will be dosed in continuous 28 day cycles, and as follows:

- Pediatric (12y- <18y): 520 mg/m^2/dose orally BID, not to exceed 800 mg orally twice daily
- Adult: ( $\geq 18$ y): 800 mg orally BID (flat dose for adults)

Surveillance imaging of primary and metastatic sites will be performed every 2 cycles, +/- 7 days after Cycle 1 Day 1, until disease progression or death. ctDNA testing results will be collected whenever performed per standard of care.

Response to treatment will be evaluated via RECIST 1.1. Treatment with Tazemetostat will continue until disease progression, unacceptable toxicity or withdrawal of consent or termination of study. Screening data will be reviewed to determine subject eligibility. Subjects who meet all inclusion criteria and none of the exclusion criteria will be entered into the study.

Total duration of subject participation will be 24 months. Total duration of the study is expected to be 36 months.

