### 8.3 Replacement of Subjects

Subjects may be replaced if they are not screen failures, have not completed at least 75% of intended doses in the first cycle, or are not discontinued for disease progression, toxicity, or any of the reasons listed in section 8.2.

Subjects who receive at least 75% of the intended doses in their first cycle will be evaluable for clinical response. Additionally, subjects who receive any dose will be evaluable for toxicity.

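### The plan does not say which 29 subjects the 10-of-29 rule uses, and gives no cut-off if more than 29 are analysed

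*Combined protocol and SAP*

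**What the plan says.** Two descriptions of the decision set stand in the current text.

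**Accrued, intent-to-treat.** Section 12.2 accrues 9 patients, stops if 2 or fewer respond, and then says: "Otherwise, 20 additional patients will be accrued for a total of 29". The test is: "The null hypothesis will be rejected if 10 or more responses are observed in 29 subjects". It states 5% type I error at a 21% response rate and 80% power at 45%. Section 12.3 says that the ORR analysis "is based on the intent-to-treat approach", with this denominator: "ORR will be calculated as the proportion of the patients with objective response divided by the total number of the study patients".

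**Evaluable.** The schema gives the accrual goal as "29 evaluable subjects (Up to 50 total accrued"). The synopsis says "Up to 50 people will be enrolled in this study to achieve 29 evaluable subjects", and 4.1 repeats it. Section 3.1 says "We plan to accrue up to 50 subjects in order to meet our goal of 29 evaluable subjects". Section 8.3 supplies the definition: "Subjects who receive at least 75% of the intended doses in their first cycle will be evaluable for clinical response". It adds a replacement sentence whose conditions are joined by an or.

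Section 12.7 places the interim look after the first 9 subjects have been enrolled and have response data. That can be read as timing or as selection. No section links the accrual goal to the cut-offs, and none gives a cut-off for more than 29.

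**The concern.** The two descriptions treat an early failure differently. The 75% dosing threshold is settled within the 28 days of cycle 1, whereas on-treatment imaging is scheduled every 2 cycles. A subject who stops in cycle 1 for progression or toxicity can therefore be non-evaluable before any scheduled scan. Under intent-to-treat that subject is a non-responder; in an evaluable set the subject disappears and enrolment continues.

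The verdict can turn on this. Suppose that 30 are enrolled, one of the first 29 stops early in cycle 1, 10 of the others respond including the 30th, and stage 1 is passed.

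- First 29 accrued: 9 responses, null not rejected.
- First 29 evaluable: 10 responses, null rejected.
- Section 12.3 read literally: 10 of 30, for which the plan has no rule.

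In an open-label, single-arm trial this choice has to be fixed before responses are known.

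**Working it through.** **Inputs from 12.2:** p0 = 0.21, p1 = 0.45, n1 = 9, continue if X1 ≥ 3, n = 29, reject if the total is ≥ 10. The ceiling of 50 comes from the schema, synopsis, 3.1 and 4.1. The documents give no non-evaluable rate, so every rate f below is an assumption.

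**Formula.** P(reject) = Σ over x = 3 to 9 of P(X1 = x) × P(X2 ≥ c − x), with X1 ~ Bin(9, p), X2 ~ Bin(N − 9, p), c the cut-off and N the total analysed.

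**Step 1: the plan's own figures (N = 29, c = 10).** At p = 0.21 the terms for x = 3, 4, 5, 6 and 7 are 0.0203, 0.0173, 0.0083, 0.0022 and 0.0003; x = 8 and 9 are negligible. The sum is 0.0485. At p = 0.45 the result is 0.804. A search at these rates with alpha ≤ 0.05 and power ≥ 0.80 returns this same design as optimal. The stated 5% and 80% are right for a fixed 29 if both rates refer to that set.

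**Step 2: literal 12.3.** All enrolled subjects are analysed, stage 1 is unchanged, and the only printed cut-off (10) is kept:

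| N analysed | Type I error at p = 0.21 |
|---|---|
| 29 | 0.0485 |
| 30 | 0.057 |
| 32 | 0.077 |
| 35 | 0.108 |
| 50 | 0.239 |

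**Step 3: cut-offs applied to 29 evaluable subjects (illustrative).** Assume that 21% is the null rate in all treated subjects and that every excluded subject is a non-responder. The rate among evaluable subjects is then 0.21/(1 − f):

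| f excluded | 0.21/(1 − f) | Type I error |
|---|---|---|
| 1 in 30 | 0.2172 | 0.059 |
| 5% | 0.2211 | 0.065 |
| 10% | 0.2333 | 0.088 |
| 20% | 0.2625 | 0.159 |

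If half of the excluded are certain failures and the other half would respond at the evaluable rate, the rate is 0.21/(1 − f/2). Type I error is then 0.056, 0.065 and 0.088 at 5%, 10% and 20%. If the null is defined on evaluable subjects, it stays at 0.0485 whatever f is.

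**Step 4: the opposite mismatch.** If 21% and 45% refer to evaluable subjects but 29 accrued are analysed with the rest as non-responders, the rates become 0.21(1 − f) and 0.45(1 − f). At f = 5%, 10% and 20%, alpha is 0.036, 0.025 and 0.012, and power is 0.75, 0.68 and 0.52.

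**The case against.** The best defence is that 12.3 already governs. It alone defines the primary analysis set; the other passages state accrual goals, and none says that ORR or the cut-offs are computed on evaluable subjects. This stands to the extent that a reader should not infer that the plan has adopted an evaluable-only test. It does not close the gap: if 4.1 is followed and more than 29 are enrolled, 12.3 supplies a denominator for which 12.2 has no cut-off.

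A second defence is that the allowance up to 50 covers screen failures. Section 5 requires eligibility to be verified before enrolment and 8.1 records screen failures separately, so this does not fit. Even if it did, 8.3 would still define evaluable by dosing.

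A third is that 8.3 bars replacement after progression, toxicity or any reason listed in 8.2. That is one reading of an ambiguous sentence. If it is right, few early failures would be replaced and the Step 3 figures shrink. The evaluability sentence itself makes no exception for such subjects.

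A fourth is that excluded subjects need not be non-responders. This is correct. Sections 7.6.2 and 7.6.4 allow a hold with resumption within 14 days. A 14-day hold in a 28-day cycle leaves about 14/28 = 50% of doses, so the subject is non-evaluable under 8.3 yet still on treatment and able to respond.

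**Conclusion.** Wrong as written: the sections conflict over the primary decision set, and the choice can reverse the primary conclusion. That rests on the text and needs no assumed rate.

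The size is conditional. The Step 2 figures need only that more than 29 are analysed with the cut-off left at 10. The Step 3 figures need three things together: cut-offs applied to evaluable subjects, a 21% null that refers to all treated subjects, and excluded subjects who are all non-responders at an assumed rate.

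Three stronger readings are tempting, and the documents do not support them:

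- That the 5% and 80% are miscalculated. They reproduce exactly for a fixed 29.
- That the trial's type I error is in fact 0.159 or 0.239. No non-evaluable rate is given, and 50 is only a ceiling.
- That the evaluable reading has been shown to favour the drug. If every excluded subject is a non-responder, any disagreement must favour rejection, because dropping non-responders cannot lower the count at either stage. That follows from the assumption and is not evidence about this trial.

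**What to change.** Name one decision set for the interim look, the 10-of-29 rule and the reported ORR with its confidence interval: the first 9 and the first 29 consecutive subjects, under the intent-to-treat principle already in 12.3. Count subjects without a documented response as non-responders, and do not replace them in the decision set. Also:

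- State how subjects who are enrolled but never dosed are handled (possible under section 6 when a recheck laboratory value fails).
- State which population 21% and 45% refer to.
- Redraft the 8.3 replacement sentence to agree, and keep the 75%-of-doses set as a sensitivity analysis.
- Change every place where the rule appears: schema, synopsis accrual goal and sample-size text, 3.1, 4.1, 8.3, 12.2, 12.3 and 12.7. A partial edit would leave the contradiction in place.

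Only if more than 29 will be analysed, pre-specify cut-offs that hold type I error at or below 5% with stage 1 unchanged: 11 for N = 30–33, 12 for 34–37, 13 for 38–41, 14 for 42–45, 15 for 46–49 and 16 for N = 50. Power at 45% is then below 80% at N = 30 (0.774), 31 (0.793) and 34 (0.799), and at least 0.808 at every other N up to 50.

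The cost is wording, with no extra patients. The possible price is power: if 45% was meant for evaluable subjects, the Step 4 power figures apply to the 29 accrued.
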